4 TRIAL DESIGN

We will conduct a two-group pragmatic encouragement clinical trial comparing the intervention and control at multiple sites. The follow up period for the trial will be 6 months.

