All primary analyses will follow an intent-to-treat approach, including all individuals assigned to an intervention arm regardless of the amount of intervention received. Non-inferiority evaluations will also be evaluated in a supplementary “as treated” analysis, comparing outcomes according to treatments actually received by patients during their observed period of follow-up. This supplemental comparison is useful in a non-inferiority assessment due to the fact that the alternative hypothesis of “no effect” is more likely in the presence of protocol violations and therefore the intent to treat approach will be anti-

conservative if many patients in the intervention arm, for example, revert to control. Also, non-inferiority of Emergency Department visit rate in the intervention arm compared to usual care control will only be assessed on final analysis if superiority is shown for the primary endpoint of no antipsychotic use at 6 months.

We will use Poisson regression to estimate (1) the percent of individuals using antipsychotics at 6 months post enrollment and (2) the total number of person-months of antipsychotic use by youth in the six month follow-up period, per provider medication orders, in each of the study arms. We will use generalized estimating equations(43) to estimate the parameters in the Poisson regression model. We will use the robust sandwich estimator to ensure correct standard errors for the intervention effect due to possible violation of the Poisson variance assumption(44); additionally, this will allow us to account for any clustering within clinics(43) and providers. Poisson regression allows comparison of relative incident rates among the intervention arms when outcomes are not rare(45). Additionally, Poisson regression will allow us to control for pre-specified baseline covariates (age, gender, and race) as well as site differences in any antipsychotic use and allow for straightforward estimation of site-specific intervention effects in sensitivity analyses. For a secondary analysis, we will repeat this approach defining antipsychotic use with prescription fill data rather than orders.

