divided by the rate on control, estimated by Poisson regression) and 95% two-sided confidence interval (CI) will be compared to the non-inferiority margin (overall: $M = 1.5$) and non-inferiority of the algorithm approach will be declared if the entire coverage of the 95% CI is less than 1.5.

In safety review reports, the ratio between arms of emergency department visit rates will be accompanied by a confidence interval and by the non-inferiority margin, 1.5, for reference. Confidence intervals will be defined by estimating the rate ratio in 5,000 bootstrap samples. Resampling will be done on the cluster (provider) level and stratified by the presence of any event within each cluster. Quantile-based confidence intervals will be identified using the appropriate percentile corresponding to the Pocock alpha-spending function for interim analyses. Excess harm is observed if the entire coverage of the confidence interval for the rate ratio comparing the greater to the lesser rate of emergency department and urgent care visits is greater than 1.5. (While the final non-inferiority analysis for this safety outcome will use the robust sandwich estimator to ensure correct standard errors, the properties of this estimator are based on asymptotic behavior and small sample size performance may be poor.)

We anticipate initial follow-up of 800 patients, randomized to the two arms, with 720 patients remaining enrolled in the study at 6 months of follow-up (i.e., 10% lost to follow-up). Assuming a $P < 0.05$ alpha level, and based on an anticipated 95% of patients in the control arm using antipsychotics at 6 months, this sample will ensure over 95% power to detect a 6% reduction in the percent of participants with any order for antipsychotic medications at 6 months. Furthermore, we expect to have 80% power to detect a 13% reduction in subgroups with exposures occurring with 25% prevalence, and 80% power to detect a 17% reduction in subgroups with exposures occurring with 18% prevalence (e.g., racial/ethnic minorities). A minimal clinically important difference of 10% was pre-specified to allow for evaluation of clinical significance as well as statistical significance. We have over 90% power to detect a 10% reduction in antipsychotic use at 6 months for patients in the intervention arm given a rate of 85%, 90%, or 95% use in the control arm.

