As these power calculations are based on the assumed percent of participants on any antipsychotic in the control arm and assumed pattern of intervention effects, we provide examples of detectable intervention effects corresponding to alternative scenarios in the table that follows, including varying rates of subgroup prevalence to evaluate power regarding intervention effectiveness in less prevalent minority groups. In summary, at a range of percentages of participants with any antipsychotic use in the control arm, we will have excellent power to detect a variety of clinically meaningful intervention effects within the expected range.

Using an estimated rate of emergency department visits of 0.0325 per month on control(47) and with a one-sided 0.025 alpha level with equal allocation between groups, we estimate 71% power(48) with 400 patients per arm and 67% power with 360 patients per arm (allowing for loss to follow-up) respectively, to detect equality of emergency department visit rates (i.e., a true rate ratio of 1) in a non-inferiority evaluation with a margin of 1.5. With a greater monthly emergency department rate of 0.05, we would have 88% and 84% power with 400 and 360 patients per arm respectively under otherwise equivalent conditions.

Power under varying percentages of participants in each arm taking antipsychotic medication at 6 months (based on medication orders) and under various subgroup prevalence assumptions.

Subgroup prevalence	n per arm*	Intervention	Control	Power
100%	360	89%	95%	80%
100%	360	85%	95%	>99%
100%	360	80%	90%	97%
100%	360	75%	85%	92%
25%	90	82%	95%	80%
18%	65	78%	95%	80%
10%	36	75%	95%	67%
5%	18	65%	95%	62%

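### The printed emergency-department non-inferiority power ignores the protocol's superiority gate, so under that rule it is an upper bound; the SAP states the test with no gate

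*Protocol*

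**What the plan says.** Protocol section 8.2.1 sets a two-stage rule for ED visits. The first stage is a gate: the non-inferiority comparison "will only be assessed on final analysis if superiority is shown for the primary endpoint of no antipsychotic use at 6 months". The second is the comparison itself: "non-inferiority of the algorithm approach will be declared if the entire coverage of the 95% CI is less than 1.5".

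Later in the same section the power is stated for a true rate ratio of 1 and a margin of 1.5, "with a one-sided 0.025 alpha level with equal allocation between groups". At 0.0325 visits per month on control, "we estimate 71% power(48) with 400 patients per arm and 67% power with 360 patients per arm (allowing for loss to follow-up) respectively". It continues: "With a greater monthly emergency department rate of 0.05, we would have 88% and 84% power with 400 and 360 patients per arm". The gate is not mentioned there.

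For the gate's own power at 89% versus 95% antipsychotic use, the protocol gives two answers. The text of section 8.2.1 claims more than 95%; the table that closes the section gives 80% with 360 per arm. The text also names a minimal clinically important difference of 10 points, for which the three full-sample table rows show above 99%, 97% and 92%.

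The SAP, under Secondary analysis I, concludes non-inferiority when the whole 95% interval lies below 1.5. It has no gate there or elsewhere.

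**The concern.** Power should describe the decision rule that will be used. Under the protocol's rule, a truly non-inferior intervention is declared so only if both stages succeed. The printed figures describe the second stage alone, so they equal the power of the full rule only if the first stage is certain to succeed.

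This is the only safety outcome with a stated power, and at the expected visit rate that power is already below 80%. Someone planning or reading the trial will take 67–71% as the chance that equal ED rates lead to a non-inferiority conclusion. If the gate applies, the absence of that conclusion may simply mean the antipsychotic-use comparison missed significance, and it would happen more often than the protocol implies.

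**Working it through.** **Inputs from the documents.** One-sided alpha 0.025, equal allocation, margin 1.5, true rate ratio 1, rates 0.0325 and 0.05 per month, and gate powers from text and table (protocol 8.2.1). Follow-up: "The follow up period for the trial will be 6 months" (protocol section 4). 400 per arm enrolled and 360 at 6 months (section 8.1). **Assumed:** a two-sided 0.05 gate test, and no clustering.

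**Step 1: reproduce the printed ED power.** Power = Φ[ln 1.5 / √(2/m) − 1.96], where m = n × rate × 6 is the expected number of events per arm.
- 0.0325, n = 400: m = 78; 0.4055/0.1601 − 1.96 = 0.572; power 71.6% (printed 71%).
- 0.0325, n = 360: m = 70.2; 0.4055/0.1688 − 1.96 = 0.442; power 67.1% (printed 67%).
- 0.05, n = 400: m = 120; power 88.1% (printed 88%).
- 0.05, n = 360: m = 108; power 84.6% (printed 84%).

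All four reproduce with no term for the gate.

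**Step 2: power of the gate at 89% versus 95%.** Two-proportion normal formula, n = 360: [0.06 − 1.96 × √(2 × 0.92 × 0.08/360)] / √[(0.89 × 0.11 + 0.95 × 0.05)/360] = 0.0204/0.0201 = 1.013, giving 84.5%. Unpooled variance gives 84.8%; a continuity correction gives 80.9%. The table's 80% is close to the last. The text's figure of more than 95% does not reproduce. With n = 400 the range from continuity-corrected to pooled is 85.2–88.0%.

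**Step 3: the two-stage rule under independence, same n in both tests, 0.0325 per month.** Joint power = gate power × ED power.

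| Antipsychotic use | Gate, 360 | Joint, 360 | Gate, 400 | Joint, 400 |
|---|---|---|---|---|
| 89% v 95% | 80–84.5% | 54–57% | 85.2–88.0% | 61–63% |
| 75% v 85% | 92% | 62% | 94.4% | 68% |
| 80% v 90% | 97% | 65% | 97.8% | 70% |
| 85% v 95% | 99.5% | 67% | 99.7% | 71% |

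In the first row at 360, 0.80 × 0.67 = 0.536 and 0.845 × 0.671 = 0.567; at 400, 0.852 × 0.716 = 0.610 and 0.880 × 0.716 = 0.630. In the 10-point rows the 360 gates are the table's, with its entry of above 99% taken as the recomputed 99.5%; the 400 gates are recomputed with pooled variance.

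At 0.05 visits per month and 89% versus 95%, the same product gives about 68–72% at 360 per arm (against 84.6% ungated).

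**Step 4: without independence.** For any dependence, joint power lies between (gate + ED − 100%) and the smaller of the two. With an 80% gate and 67% ED power: 80 + 67 − 100 = 47%, up to 67%. A bivariate-normal check with correlation from −0.3 to +0.5 between the test statistics gives about 52–62% at 360 per arm.

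**The case against.** The printed numbers are not wrong. The protocol states exactly what they are computed for: a non-inferiority evaluation with given rate, margin, alpha and n. Quoting power test by test in a sequence is a legitimate reporting choice. A reader might infer that 71% and 67% were miscalculated; Step 1 rules that out.

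The SAP's rule has no gate, so under the SAP as written 67–71% is the right power. This stands, and it makes the disagreement between the documents part of the point.

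The size depends on inputs the documents leave open. If the text's gate power of 95% is used instead of the table's 80%, the product is 64% at 360 per arm (0.95 × 0.67) and 67% with the 71% ED figure. That gate power does not reproduce, but the conflict is the protocol's to resolve. A reader might also quote a single range of 54–60%. Its upper end multiplies a gate at 360 per arm (84.5%) by ED power at 400 (71%), which mixes sample sizes. It also needs independence, which cannot be checked: both outcomes come from the same patients and providers, and no correlation is given.

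The 6-point scenario is the least favourable of the four full-sample rows. At the 10-point difference that the protocol calls minimally important, the gate costs little.

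Finally, a reader might infer that a failed gate leaves ED safety unexamined. It does not. Protocol section 8.2 commits to comparing ED visits and other harms between arms, and sections 8.2.1 and 10.1 provide comparisons to the monitoring board, none of them gated. Only the formal non-inferiority conclusion is lost.

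**Conclusion.** The point holds as one of labelling and consistency. Under the protocol's rule, the four printed ED powers are upper bounds, whatever the dependence between the tests. Under the SAP's rule they stand.

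If the gate applies, the loss at 0.0325 visits per month is material for 89% versus 95%: roughly 10–13 points at 360 per arm and 9–11 at 400, assuming independence. It is about 0 to 5 points at the 10-point difference. The bounds of 47–67% at 360 per arm need no independence assumption but do take the table's 80% gate.

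None of these figures, printed or recomputed, allows for clustering by provider, for which the documents give no intracluster correlation. The SAP also counts urgent care visits, so its event rate may differ from the one used for power.

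**What to change.** 1. Reconcile protocol section 8.2.1 with SAP Secondary analysis I on whether the superiority gate applies to the ED comparison.
2. If it applies, state it in the SAP and label the 71%, 67%, 88% and 84% as conditional on passing the gate, with the dependence assumption this needs. Beside them print the power of the full two-stage rule for each full-sample row of the table, using the same n for both tests and giving the independence assumption and the bounds. If it does not apply, delete the gate from the protocol; the printed figures then stand and should be described as ungated.
3. Before using either as the gate power, reconcile the text's figure of more than 95% with the table's 80% for 89% versus 95% (recomputed 81–85% at 360 per arm).

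The cost is wording and one extra table column, with no added patients or data. If the gate is kept, the stated safety power becomes less favourable.

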8.3 Handling of Missing Data

All outcomes for this trial will be collected from electronic health records, which means traditional study drop out will not result in missing information. It is possible for youth to disenroll from a health care plan in the 6 months following initial randomization. Patients who disenroll from the health system are lost to follow up data collection.

As described above, we will assess the association of baseline characteristics and the probability of remaining enrolled in the same health care plan for the full 6 month follow-up. If there are large differences between the rate of full follow-up by baseline characteristics we will perform sensitivity analyses including these covariates in Poisson regression models to evaluate if missing this missing information has led to biased effect estimates. Our primary analyses will use an offset term(46) in the Poisson regression models in order to include all individuals regardless of the length of follow-up. We have performed conservative power calculations assuming that all individuals without a full 6 months of follow-up will be excluded from analyses. If disenrollment rate is high than anticipate or there is missing information in important baseline characteristics we will use multiple imputation(49) or weighted(50) estimates to ensure that our results are not biased due to missing data.

One study site (NCH) does not have complete prescription fill data because they serve patients in their clinics who are not enrolled in the insurance product for their health plan. Complete capture of prescription fill data does not differ with study arm assignment, thus, we do not expect estimates of the interventions effect to be biased. However, missing prescription fill data could lead to underestimates

of the percentage of youth taking antipsychotics at 6 months and/or the percentage of youth who fill prescriptions for lower risk, first line medications. We will conduct quality assurance checks comparing the number of medication orders and prescription fills by individual across all sites to determine degree to which medication order and prescription fill data differ.

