8 STATISTICAL CONSIDERATIONS

8.1 Sample Size Considerations

We anticipate enrolling as many as 800 eligible patients in the trial (up to 400 per arm), with up to 360 eligible patients in each arm remaining enrolled at 6 months of follow-up (i.e., 10% lost to follow-up).

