Data for our primary outcome of interest, any antipsychotic use, will be collected from electronic health records on provider orders. Electronic health record data on prescription fills will be used to assess the secondary outcome (antipsychotic medication fills). This means that traditional study drop-out due to premature participant withdrawal from the study will not lead to missing data in primary analyses. However, there will be the potential for differential follow-up rates among individuals due to youth disenrolling from their or their parent/guardian's health plan. Death is also a possibility, but unlikely. We will compare those youth for whom we are only able to collect outcome information for a portion of the 6 month follow-up period to those participants for whom we have complete 6 month follow-up information on their demographics, treatment group, and other salient baseline variables. We will account for differential follow-up times due to disenrollment in the Poisson regression model using an offset(46). Because our power calculations are based on excluding all individuals lost-to-follow-up due to disenrollment, these estimates are conservative.

The secondary outcome of emergency department visits will be estimated by Poisson regression in each of the arms, again using generalized estimating equations for the reasons listed above for the primary outcome. The intervention will be compared for non-inferiority to control using a margin of $M=1.5$. This margin of 1.5 for the rate ratio represents a threshold for the relative increase of 50%, beyond which we would consider unacceptable. Sikirica (2014) observed an annual rate of 0.39 per year among adolescents with attention deficit/hyperactivity disorder who were taking antipsychotics(47). Using an estimated rate of emergency department visits of 0.0325 per month on control(47), the non-inferiority margin of 1.5 for the incidence rate ratio would represent a corresponding maximum acceptable rate of 0.0488 per month in the intervention arm. If the rate of emergency department use is greater than expected, say 0.05, then the non-inferiority margin of 1.5 would correspond to a maximum rate of 0.075 in the intervention arm. The estimated treatment effect (emergency department rate on algorithm

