Patient enrollment in the study occurs when a provider writes a qualifying antipsychotic prescription for an eligible adolescent patient or enters a patient reported medication (these two actions are indistinguishable in Epic). (Eligibility is confirmed by study staff following enrollment.) Follow-up time after enrollment extends for 6 months (181 days). Some patients will not remain enrolled in the health plan for a full six months, censoring follow-up, and the number of days covered in the health plan post-study enrollment should be recorded. If patients have a health care plan enrollment gap that is less than 45 days, they will be considered as having continuous enrollment in the study (i.e. not loss to follow up). For example, if a patient has a gap in their healthcare plan enrollment for less than 45 days during the study, this patient will be considered to have continuous enrollment. However, if there is an enrollment gap in their healthcare plan for at least 45 days, the patient will be disenrolled from the study at the healthcare plan disenrollment day. Note that, since patients do not have to be enrolled with a specific health care plan to be seen at NCH, we will assume a full follow up time of 6 months (181 days). Follow-up time should be indicated in the analytic dataset for all enrolled patients.

Analysis

Primary analysis I

Our primary analysis examines the percentage of patients taking antipsychotic medications (measured by provider medication orders) at 6 months post enrollment

Descriptive analysis will summarize **the percent of patients observed to be using AP at 6 months**, defined by presence of days' supply AP ≥ 181 days or medication in hand at 6 months. For example, if a patient has a 30-day supply order on or after 151 days post-enrollment, that patient has AP medication "in hand" at 6 months. Note: a patient does not have to have ≥ 181 days' total supply during the study to have medication in hand at 6 months. We will not adjust for loss to follow-up or disenrollment for this outcome definition. Patients who do not have prescription fill information up to 6 months post-baseline due to health plan disenrollment will have AP use observed at 6 months if they have AP orders after disenrollment that is ≥ 181 days. For example, if a patient disenrolls at day 160 and has a AP order (30 days' supply) after disenrollment, they have medication "in hand" at 6 months

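### The protocol's follow-up-time offset does not suit the yes/no outcome of antipsychotic use at 6 months, and the SAP analyses that primary outcome by an incompatible rule

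*Protocol*

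**What the plan says.** Protocol Section 8.2.1 names one model for both primary outcomes: "We will use Poisson regression to estimate (1) the percent of individuals using antipsychotics at 6 months post enrollment", followed by person-months as item (2). A later paragraph of that section, which opens on any antipsychotic use as the primary outcome, adds: "We will account for differential follow-up times due to disenrollment in the Poisson regression model using an offset(46". Section 8.3 repeats the rule for the primary analyses in general ("Our primary analyses will use an offset term(46) in the Poisson regression models in order to include all individuals"). Neither place exempts the yes/no outcome. Section 8.3 also says that patients who disenroll are lost to data collection, and the protocol does not say how their 6-month status is coded.

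On power, Section 8.3 states: "We have performed conservative power calculations assuming that all individuals without a full 6 months of follow-up will be excluded from analyses".

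The SAP, last updated 12/17/2021, differs. Under Primary analysis I, use at 6 months is analysed by logistic GEE with arm and prior hospitalization as the only covariates and no offset. On leavers it says: "We will not adjust for loss to follow-up or disenrollment for this outcome definition". Orders placed after disenrollment count as use if they cover day 181. The SAP keeps an offset for days of supply (Primary analysis II) and for emergency and urgent care visits (Secondary analysis I).

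**The concern.** In a Poisson model, an offset for follow-up time makes the expected outcome proportional to that time. This suits person-months and visit counts. It does not suit a status at one time point: a child who leaves on day 60 of 180 is not one third as likely to be using at 6 months, and under the protocol that status was not seen. Whatever value is entered for such a child, the model no longer estimates the percent using at 6 months.

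Three things are at stake: the reported percentage, the protocol's assurance that its power is conservative because leavers were left out of the calculation, and protection against a false effect if disenrollment differs between arms. In addition, one primary outcome has two specifications, a rate ratio with an offset and an odds ratio without one.

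**Working it through.** **Inputs from the protocol.** Section 8.1: 800 patients, 400 per arm; 10% loss, which leaves 360 per arm at 6 months. Section 8.2.1: control use 95%, alpha 0.05, and a table row of 360 per arm, 89% versus 95%, power 80%.

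**Assumptions not in the documents.** Independent patients (no provider clustering). Leavers are coded either as not using or at their status on exit. In the second case, use falls linearly from 100% at enrollment to its 6-month value. Exits are uniform over follow-up, all in the first half, or all in the second half. Loss and use are unrelated.

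**The plan's own figure.** Two-sided pooled test, 360 per arm: null SE = √(2 × 0.92 × 0.08 / 360) = 0.0202; alternative SE = √((0.95 × 0.05 + 0.89 × 0.11) / 360) = 0.0201; power = Φ((0.06 − 1.96 × 0.0202) / 0.0201) = 84.5%. With a continuity correction it is 80.9%, so the table's 80% is reproduced that way. The text of Section 8.2.1 gives over 95% for the same effect. That does not reproduce: even 400 per arm gives 88.0%.

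**Reported percentage.** With arm alone in the model and working independence, the fitted value for an arm is ΣY / Σt, where t is the fraction of 6 months followed. Let p be true use, l the loss and m the mean exit fraction.

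- Leavers coded 0: p(1 − l) / (1 − l + lm)
- Status at exit kept: [p(1 − l) + l(1 − (1 − p)m)] / (1 − l + lm)

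At p = 0.95 and l = 0.10:

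| Exits | m | Coded 0 | Status kept |
|---|---|---|---|
| First half | 0.25 | 0.855/0.925 = 92.4% | 0.95375/0.925 = 103.1% |
| Uniform | 0.50 | 0.855/0.950 = 90.0% | 0.9525/0.950 = 100.3% |
| Second half | 0.75 | 0.855/0.975 = 87.7% | 0.95125/0.975 = 97.6% |

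**Ratio with equal loss and timing.** Coded 0, the common factor cancels: 0.89/0.95 = 0.937. With status kept and uniform exits it is 0.943/1.003 = 0.940. The tested ratio is essentially right.

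**Power, 95% versus 89%, 10% loss in each arm.** Simulated trials of 400 per arm, robust variance of the log rate = Σ(y − rate × t)² / (Σy)²:

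| Exits | Coded 0 | Status kept |
|---|---|---|
| First half | 81% | 60% |
| Uniform | 71% | 71% |
| Second half | 62% | 84% |

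Repeat simulations moved the ends by a point or two, giving a range of about 58% to 84%. Leaving leavers out gives 85%. For 10-point differences with uniform exits, power is about 98% (95% versus 85%), 93% (90% versus 80%) and 87% to 88% (85% versus 75%). The protocol's table has >99%, 97% and 92%, and its text promises over 90% for all three.

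**False effect, 95% use in both arms, larger loss in the intervention arm.** With uniform exits and leavers coded 0, loss of 8% versus 12% gives (0.836/0.94) / (0.874/0.96) = 0.977. Loss of 5% versus 15% gives (0.8075/0.925) / (0.9025/0.975) = 0.943. Rate ratio and total rejection rate:

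| Loss, exits | Coded 0 | Status kept |
|---|---|---|
| 8% v 12%, first half | 0.99, 10% | 1.03, 28% |
| 8% v 12%, uniform | 0.98, 18% | 1.02, 18% |
| 8% v 12%, second half | 0.97, 28% | 1.01, 10% |
| 5% v 15%, first half | 0.97, 36% | 1.09, 95% |
| 5% v 15%, uniform | 0.94, 76% | 1.06, 76% |
| 5% v 15%, second half | 0.92, 93% | 1.03, 35% |

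Leaving leavers out gives 5% in both loss scenarios. With 85% use and uniform exits, 8% versus 12% gives about 10% to 12%.

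**SAP rule, worst case.** If no leaver has a later order and all count as non-users, 10% loss turns 95% versus 89% into 85.5% versus 80.1%. Power with 400 per arm is then 52.5%. With no true effect at 95% use, a false benefit appears in 33% of trials (8% versus 12%) or 96% (5% versus 15%).

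**The case against.** The strongest reply is that the later SAP already drops the offset for this outcome. A reader might infer that the trial's primary result will carry the offset error, with percentages above 100% and offset-driven false effects. The documents do not support that, because the SAP's analysis contains no offset here. What stands is an unreconciled protocol rule and two incompatible specifications.

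A reader might also infer that power must fall below the stated figure. It need not. Two cells of the power table reach the 80% in the protocol's table, and at the protocol's minimal important difference of 10 points the loss is small except at 85% versus 75%. Nor does a modest imbalance create an effect of the size sought: 8% versus 12% gives a ratio of 0.97 to 1.03, against a target of 0.937. A ratio near the target needs roughly 5% versus 15%, which nothing in the documents predicts. The direction depends on leaver coding and can run against the intervention.

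The protocol does have safeguards. Section 8.2.1 compares leavers with completers, including by treatment group, but attaches no consequence to the result. The covariate sensitivity analyses in Section 8.3 stay within the Poisson models. Multiple imputation or weighting is triggered by higher disenrollment than anticipated or by missing baseline data. Both unequal-loss scenarios average the anticipated 10%, so neither trigger need fire.

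**Conclusion.** The point holds as a defect in the protocol's wording and a conflict with the SAP. The offset is wrong in kind for a status at 6 months and, as written, would report a true 95% as about 88% to 103%. With equal loss and timing the comparison between arms is essentially unbiased, but the claim of conservative power is not assured (about 58% to 84%, against about 85% with leavers excluded and 80% in the table). With no true effect, false positives would be about 10% to 28% at 8% versus 12% loss and about 35% to 95% at 5% versus 15%.

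All these figures depend on the assumed leaver coding, exit timing, loss split and independence. It would be too strong to say that the conservative claim is simply false, or that the planned primary analysis is invalid because of the offset. Nor does adopting the SAP rule unchanged settle the matter, since its treatment of leavers without later orders can, in the worst case, cost more power than the offset.

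**What to change.** In protocol Sections 8.2.1 and 8.3, restrict the offset to person-months and to emergency and urgent care counts. For use at 6 months, fit the model without an offset to patients whose 6-month status is observed. Handle unobserved leavers, at any loss rate, by a method Section 8.3 already cites: inverse-probability weighting or multiple imputation, using arm, site and baseline covariates. Either is sound; one should be named as primary.

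State the same model and rule under Primary analysis I of the SAP, including how leavers without later orders are treated. Define observed status by enrollment at 6 months. If it is defined by the presence of a later order, only leavers who are users would count as observed. Keep the word conservative only if the stated power refers to that analysis, and reconcile the 80% and over-95% figures for the same 6-point effect.

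The cost is wording in both documents and one additional model on data already held, with a slightly wider confidence interval.
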